**Hyperpolarized Xenon gas MR Imaging in Radiotherapy**

The following information will be recorded: description, date of onset and end date, severity, assessment of relatedness to trial medication, other suspect drug or device and action taken. Follow-up information should be provided as necessary.

The severity of events will be assessed on the following scale: 1 = mild, 2 = moderate, 3 = severe.

AEs considered related to inhaled xenon as judged by a medically qualified investigator or the Sponsor will be followed either until resolution, or the event is considered stable.

It will be left to the investigator's clinical judgment whether or not an AE/ AR is of sufficient severity to require the patient's removal from Xe-129 MRI scanning. A patient may also voluntarily withdraw from study procedures if they tolerate it poorly. Further details of withdrawal are presented in Section 9.8.

In the event of symptoms arising, patients will be given appropriate care and medical supervision until symptoms resolve, or the condition becomes stable. Every effort will be made to gather outcome data on patients through study follow-up, or general practitioner/ hospital staff unless the patient is specifically withdrawn consent to such efforts.

**11.4. Reporting Procedures for Serious Adverse Events**

All SAEs (other than those defined in the protocol as not requiring reporting) following Xe-129 lung MRI scanning must be reported on the SAE reporting form to R&D within 24 hours of the Site Study Team becoming aware of the event. R&D will perform an initial check of the report, request any additional information, and ensure it is reviewed by the Medical Monitor on a weekly basis. It will also be reviewed at the next Trial Safety Group meeting. All SAE information must be recorded on an SAE form and faxed, or scanned and emailed, to R&D. Additional and further requested information (follow-up or corrections to the original case) will be detailed on a new SAE Report Form and faxed/mailed to R&D.

**11.5. Expectedness**

Expectedness will be determined according to the Investigators' Brochure.

After breathing gas containing xenon, feelings of light-headedness, paraesthesia, euphoria or mild 'drunk' feeling are common, occurring in 9 out of 10 people. These symptoms last for just a few minutes, just like breathing 'laughing gas'. The expected adverse reactions are described in the Investigators' Brochure.

**11.6. SUSAR Reporting**

**Hyperpolarized Xenon gas MR Imaging in Radiotherapy**

All SUSARs will be reported by the CI to the relevant Competent Authority and to the REC and other parties as applicable. For fatal and life-threatening SUSARs, this will be done no later than 7 calendar days after the Sponsor or delegate is first aware of the reaction. Any additional relevant information will be reported within 8 calendar days of the initial report. All other SUSARs will be reported within 15 calendar days.

Treatment codes will be un-blinded for specific participants.

Principal Investigators will be informed of all SUSARs for the relevant IMP for all studies with the same Sponsor, whether or not the event occurred in the current study.

**11.7. Safety Monitoring Committee**

The Oxford University Hospitals Trust / University of Oxford Trials Safety Group (TSG) will conduct a review of all SAEs for the trial reported during the quarter and cumulatively. The aims of this committee include:

- To pick up any trends, such as increases in un/expected events, and take appropriate action
- To seek additional advice or information from investigators where required
- To evaluate the risk of the trial continuing and take appropriate action where necessary

**11.8. Development Safety Update Reports**

The CI will submit (in addition to the expedited reporting above) DSURs once a year throughout the clinical trial, or on request, to the Competent Authority (MHRA in the UK), Ethics Committee, Host NHS Trust and Sponsor.

## 12. STATISTICS

### 12.1. Description of Statistical Methods

Early studies (73, 78), including work from our own group (79), using Xe-129 lung MRI have demonstrated that this technique provides valuable information regarding *global* pulmonary parenchymal apparent diffusion coefficients (ADCs – measures of increased air spaces) in COPD, demonstrating important differences compared to age matched controls or young, healthy volunteers. Our scanner has excellent anatomical resolution compared to those used in most previous work, enabling us to perform *regional* analysis, down to the level of the secondary pulmonary lobule and to determine bronchial wall thickness.

The primary outcome measure for determining Xe-129 lung MRI changes following radiotherapy will be evaluating the change in Xe-129 lung MRI imaging from baseline to other time points post-radiotherapy initiation.

We will also compare *global* Xe-129 lung MRI ADC measures between patients from other diagnostic groups (initially patients with NSCLC considered suitable for surgery, patients with COPD and patients with normal lungs who are well, but who are having chest CT imaging due to a prior testicular malignancy: these studies are covered by separate consent). We will carry out the following completely novel analyses: -

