##### 4.1. Radiation induced lung toxicity (RILT)

Radiation induced lung toxicity (RILT) occurs when normal lung tissue is irradiated while treating tumours. RILT presents in two phases designated radiation pneumonitis (acute) and fibrosis (late). Radiation pneumonitis generally occurs between two and seven months after RT and may present clinically with cough, dyspnoea, fever and chest pain or with radiographic changes only. Acute pneumonitis is treated with steroids but can be life-threatening even with treatment, though with early identification and treatment most patients recover. If untreated, acute pneumonitis can progress to permanent fibrosis after more than six months. RILT has been shown to increase in frequency after increased radiation dose, increased volume of the lung irradiated, some combinations of chemotherapy and RT, previous radiation and steroid withdrawal.

The risk of developing RILT can be determined by assessment of the mean lung dose (MLD) and volume of lung receiving a dose of 5-20 Gy ( $V_{5-20}$ ) over a course of radical RT (3-10). By reducing set-up variability and tumour motion due to respiration, the planning target volume (PTV) margins can be reduced, thus reducing the amount of normal lung irradiated and potentially resulting in a lower risk of RILT.

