**4.4. Rationale for Hyperpolarized Xe-129 MR Imaging in Radiotherapy**

Hyperpolarized Xe-129 MR imaging will provide regional functional information about the lung that may be useful in predicting RILT post radiotherapy. It is feasible to co-register hyperpolarized Xe-129 MRI with RT planning scans. Incorporating information from hyperpolarized Xe-129 MR imaging into radiotherapy planning has the potential to minimise and predict RILT.

Hyperpolarized Xe-129 MR imaging offers the potential to inform the radiotherapy planning process so that parts of the lung demonstrated to function well are spared at the expense of less functional/diseased parts. This may reduce radiotherapy side effects and enable individuals who would otherwise be unsuitable for radical treatment to receive potentially curative therapy.

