## 6. OBJECTIVES AND OUTCOME MEASURES/ENDPOINTS

|           | Objectives  | Outcome Measures/Endpoints  |
|-----------|---|---|
| Primary   | To demonstrate that hyperpolarized Xe-129 is sensitive to change following pulmonary radiotherapy, and thus may be developed as an objective and quantifiable method of functional lung assessment in patients undergoing radiotherapy that affects the lung  | Change in hyperpolarized Xe-129 MR imaging from baseline to other time points post radiotherapy initiation.   |
| Secondary | 
To obtain preliminary data demonstrating if changes in hyperpolarized Xe-129 MR imaging correlate with subjective and objective responses following pulmonary radiotherapy.
 
To obtain preliminary data demonstrating if baseline hyperpolarized Xe-129 MR imaging is a more reliable clinical
 | 
Change in hyperpolarized Xe-129 MR imaging parameters from baseline to other time points post radiotherapy initiation compared to subjective and objective measures of lung function.
 
Comparison of hyperpolarized Xe-129 MR imaging and four-dimensional CT (4D-CT) at baseline.
 |

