## 7. TRIAL DESIGN

### 7.1. Summary of Study Design

This will be an open, single-centred study in the UK. The study group will include 30 patients who are considered suitable for radiotherapy that will affect the lung. Participants considered for radiotherapy that will affect the lung include those with a diagnosis of lung cancer and those with other diagnoses, for example, oesophageal cancer, chest wall tumours and lymphoma. All potential participants for this study undergo an *enrolment visit* (Visit 1). This is an opportunity to discuss the study in more detail, and for those choosing to take part to gain informed, written consent. Eligibility criteria will be checked. All female participants of child-bearing age will have had pregnancy excluded as part of their routine clinical care in Oncology prior to starting radiotherapy. Volunteers will be invited to undertake a 'dummy run' of Xe-129 lung MRI imaging, during which they lie on a couch similar to that used during the MRI, and practice the manoeuvre required when breathing in xenon from a 1L bag during subsequent lung imaging. During the dummy run this will simply be air or oxygen in the 1L bag.

The enrolment and baseline visits are compulsory for all participants. Participants will be required to complete at least one follow-up visit from the "half-way through" following commencement of radiotherapy, end of treatment and 3-months post-radiotherapy visits. The three follow-up visits will be offered to all patients, however completion of only one visit post-commencement of radiotherapy will be compulsory.

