**9.4. Randomisation, blinding and code-breaking**

This study is not a randomised trial. All patients undergoing hyperpolarized MR imaging will breathe Xe-129.

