**12.2. The Number of Participants**

The total sample size will be 30.

It is not possible to perform a detailed power calculation regarding sample size because this is the first time regional lung hyperpolarized Xe-129 MR indices have been correlated with physiological and functional outcomes in patients considered suitable for radiotherapy affecting the lung. We have taken the number of potential participants who are referred to our Oxford centre and considered suitable for radiotherapy affecting the lung over the last year into careful consideration and are confident that this sample size is feasible.

In our development work with this technology using He-3 gas, we have shown in 24 patients with COPD that hyperpolarized gas MR imaging identifies more lung regions affected by emphysema (defined from ADC values  $>0.34 \text{ cm}^2/\text{s}$ ) than does the severity of emphysema quantified by thoracic CT (defined from lung attenuation  $<960\text{HU}$ , a standard CT index).

To date most studies employing hyperpolarized Xe-129 have been on animal models and healthy volunteers and have reported it as a viable functional lung imaging modality (18, 65). The sample size proposed for this trial will be sufficient to be informative in our planned analyses and direct future investigation.

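### The primary analysis is a single-arm change from baseline with no internal comparator, and section 12 never relates change to delivered dose, so a change could not be attributed to radiotherapy

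*Combined protocol and SAP*

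**What the plan says.** The primary objective (section 6) is "To demonstrate that hyperpolarized Xe-129 is sensitive to change following pulmonary radiotherapy". The matching analysis in 12.1 is "evaluating the change in Xe-129 lung MRI imaging from baseline to other time points post-radiotherapy initiation". It names no parameter, no whole-lung or regional level, no single visit, no test and no comparator. Section 9.4 confirms the absence of a control arm: "This study is not a randomised trial". On numbers, 12.2 says "The total sample size will be 30" and "It is not possible to perform a detailed power calculation regarding sample size".

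The cohort mixes "those with a diagnosis of lung cancer and those with other diagnoses" (7.1), and 8.2 admits patients having concurrent or sequential chemoradiotherapy.

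The background points towards dose and region. Section 4.1 states that "RILT has been shown to increase in frequency after increased radiation dose, increased volume of the lung irradiated" and cites mean lung dose and a 5-20 Gy volume measure as predictors. Section 4.4 states that "It is feasible to co-register hyperpolarized Xe-129 MRI with RT planning scans". Section 9.7 says all treatment is CT planned. A secondary endpoint in section 6 compares conventional plans with plans modified by the Xe-129 information. None of this reaches the analysis of change in section 12.

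**The concern.** A before/after difference in one cohort contains everything that moved between the two scans. The plan itself shows several candidates besides radiation:

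- chemotherapy given with or around radiotherapy (8.2);
- tumour characteristics and co-morbidity, which 4.2 accepts as sources of variation in lung function;
- an inhaled mixture that may range from 50% to 100% xenon, and new sequences introduced during the study (9.5).

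Tumour response or progression can also open or close airways, and is likely to act differently in patients with and without lung cancer.

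Two errors follow. A significant change could be credited to radiotherapy when something else caused it. And if the measure is averaged over the whole lung, a null result could hide a real change confined to the irradiated part. Either would weaken the use the objective has in mind, which is to develop Xe-129 MRI for patients having radiotherapy that affects the lung.

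**Working it through.** **Does anything else in the plan act as a comparator?**
- The comparison with other diagnostic groups (12.1) concerns global ADC across separate studies. It is not a control for change over radiotherapy.
- The repeat baseline scan (9.5, 12.6) measures test-retest noise, not cause.
- Regional ADC and CT co-registration appear in 12.1 as technique development, with no link to dose.
- Lobar data are correlated with dyspnoea scores (12.1), not dose.

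So nothing does.

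**The plan's own figure.** N=30 rests on feasibility and has no inputs to reproduce. For orientation, assume a one-sample t-test on within-patient change, two-sided 0.05 (12.3 gives 0.05 without sidedness). With 30 pairs, 80% power needs a mean change of 0.53 SD; the normal approximation is (1.960+0.842)/√30 = 0.51. With 20 pairs it is 0.66 SD and with 10 pairs 1.00 SD. Fewer pairs are possible because only one of the three follow-up visits is compulsory (7.1).

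**False attribution.** Let every patient drift by δ SD with no radiation effect. The chance of p<0.05 at n=30 comes from the noncentral t with 29 df and noncentrality δ√30:

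| δ | Chance of p<0.05 |
|---|---|
| 0.2 | 18.5% |
| 0.3 | 35.5% |
| 0.5 | 75.4% |

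In a simulation (40,000 runs, n=30, 20% irradiated, correlation 0.5), drifts of 0.3 and 0.5 regional SD made the whole-lung test reject in 40.6% and 82.2% of runs. The high-minus-low contrast stayed at 5.0%, because a shared drift cancels in it.

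**Dilution, if the measure is whole-lung.** Let the irradiated share be f, the change in irradiated lung have mean 1 and SD 1, the change in spared lung have mean 0 and SD 1, and their correlation be ρ. The whole-lung mean is f, with SD √[f² + (1−f)² + 2f(1−f)ρ]. At ρ = 0.5, n = 30:

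| f | SD | Standardised effect | Power |
|---|---|---|---|
| 0.10 | √0.91 = 0.954 | 0.105 | 8.6% |
| 0.20 | √0.84 = 0.917 | 0.218 | 21.2% |
| 0.35 | √0.7725 = 0.879 | 0.398 | 55.9% |

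At ρ = 0 and f = 0.35 power is 71%. At ρ = 0.5 and f = 0.50 it is 86%. Dilution is severe for small fields and mild for large ones.

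**Power of the contrast.** Let the irradiated region's SD be s. The contrast has mean 1 and SD √(s² + 1 − 2ρs). At n = 30:

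| s | ρ | SD | Power |
|---|---|---|---|
| 1 | 0.5 | 1.000 | over 99% |
| 1 | 0 | 1.414 | 96% |
| 2 | 0.5 | 1.732 | 86% |
| 2 | 0 | 2.236 | 66% |

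A noisier region also hurts the whole-lung test. With s = 2, ρ = 0.5, f = 0.35 its SD is √(0.49 + 0.4225 + 0.455) = 1.169, the standardised effect is 0.35/1.169 = 0.299, and power is about 35%. With only 10 attending the named visit, contrast power at s = 1, ρ = 0 is 51%.

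**The case against.** **The objective is modest.** It speaks of change following radiotherapy, in a 30-patient cohort that 12.2 says is meant to inform later work, and 12.7 allows extra exploratory analyses. This stands in part: the before/after estimate is a valid description, and a reader who took it to be worthless would go too far. But the objective goes on to development for radiotherapy patients, which needs some link to radiation. An unspecified exploratory analysis is weak support for that.

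**Dilution is not established.** A reader might infer that the primary is a whole-lung mean. The plan does not say so, and 12.1 stresses regional analysis just before the primary is stated. Only the conditional claim holds.

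**Dose maps are not listed as study data.** A reader might infer that they are already to hand. The documents show CT planning (9.7), an endpoint that needs the plans (section 6), and co-registration described as feasible (4.4). Access is a reasonable inference, not a stated fact. Patients without lung cancer have no study CT (9.6, 9.9), so their registration must run through the planning CT.

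**Some nuisance causes are already reduced.** There is a dummy run (7.1), a calibration breath and a practice bag (9.5), batch polarization testing (10.2), and exclusion of interfering conditions (8.3). This stands, but none of it addresses chemotherapy or tumour change.

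**The contrast keeps local confounding.** Tumour shrinkage or progression acts in or near high-dose lung, and spared lung may compensate. This stands: the contrast reduces confounding and does not remove it.

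**Conclusion.** The gap is real and should be closed before analysis. The primary is an uncontrolled before/after change, nothing in section 12 relates change to dose, and no other planned analysis supplies a comparator. A significant result would therefore not show sensitivity to radiotherapy as distinct from chemotherapy, tumour change or acquisition. Dilution is a further risk only if the measure is a whole-lung summary.

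All power figures are illustrations on assumed SDs, correlations, irradiated fractions and a 1 SD local effect. A reader might infer that power simply falls from over 99% to 8%, 19% and 46% at irradiated shares of 10%, 20% and 35%. Those values are arithmetically right for standardised effects of 1.0, 0.10, 0.20 and 0.35. But they treat whole-lung and regional SDs as equal, and the starting value is the power for a regional change, not for the contrast. The better-matched comparison is 9%, 21% and 56% (equal regional SDs, correlation 0.5) against roughly 66% to over 99% for the contrast across the SDs and correlations tried. Both fall if fewer than 30 attend the visit.

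**What to change.** In 12.1, pre-specify a within-patient, dose-based analysis of one named regional Xe-129 parameter at one named visit:

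- **Estimate:** change in high-dose lung minus change in low-dose lung, or a regional dose-change slope in a mixed model. Exclude tumour volume.
- **Regions:** fixed cut-points applied to the planned dose distribution, for example the 20 Gy and 5 Gy levels in 4.1. If the half-way visit is named, state how dose not yet delivered is treated.
- **Data:** take the dose distribution from the radiotherapy plans already needed for the plan-comparison endpoint, and list it as study data. Register it through the planning CT and proton MRI, which also covers patients without lung cancer.
- **Use:** base any claim of sensitivity to radiotherapy on this contrast. Report the overall before/after change alongside as descriptive, and show both by lung cancer versus other diagnosis.

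No new scan, visit or patient is needed, and treatment is unaffected. The cost is analysis time and plan export. The downsides are registration error at dose boundaries, noisier small regions, and possible compensation in spared lung. The contrast removes patient-wide and session-wide influences to the extent that both regions share them. Local tumour effects remain and should be stated as a limitation.

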#### Technique development

- Assessments of detailed regional data, with regional ADC and bronchial wall thickness measurements.
- Accurate co-registration of *global* and *regional* data from Xe-129 lung MRI and chest CT, by correlating lung masks obtained from CT and proton MRI scans. Analysis of the correlation of MRI ADCs with CT lung tissue density (measured in Hounsfield units).
- Development of perfusion data (blood flow through the lungs) obtained using dissolved phase Xe-129 lung MRI, and validation against the current gold standard – ventilation/perfusion nuclear medicine scanning.
- Development of novel and automated analysis methods, based on computational models of lung function and combined anatomical and functional information from CT and MRI scans, following current work at the Computational Biology Group.
- Comparison of hyperpolarized Xe-129 MR imaging and four-dimensional CT (4D-CT) at baseline.

#### Demonstration of superiority over standard lung function assessment tools

- Multivariate analysis to correlate global and regional (lobar) data from Xe-129 lung MRI with key patient-centred outcome measures – dyspnoea assessment using the Dyspnoea-

**Hyperpolarized Xenon gas MR Imaging in Radiotherapy**

12 score (70) and MRC breathlessness score. We will test the hypothesis that Xe-129 lung MRI has a closer correlation with these measures than FEV1 or gas transfer.

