**4.3. Current pulmonary functional imaging is limited**

Currently assessment of patients for radiotherapy involves lung function measurements to provide a clinical indicator as to whether or not the patient would tolerate treatment and maintain sufficient functioning lung post-treatment to continue with activities of daily living without significant impairment. The current gold standard for assessment of lung function is spirometry and gas transfer. Spirometry and gas transfer reflect *global* lung function but provides no information about the different regions of the lung or regarding the support 'framework' of the lung, the parenchyma. Changes in lung function as measured by spirometry do not coherently correlate with symptom severity or reflect a decline in patient health (13). This weak relationship is probably because the lung is a complex regional organ where localized disturbances of a variety of factors including gas flow (ventilation), blood flow (perfusion) and gas transfer all combine to impair respiratory function.

Some imaging techniques can detect regional lung health, however each has limitations. Computed X-ray tomography (CT) provides structural, rather than functional readout and exposes patients to both radiation and contrast. FDG-PET provides an individualized estimate of radiation response, but not pulmonary function information. Scintigraphy (SPECT) with radioactive gas, can

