**Hyperpolarized Xenon gas MR Imaging in Radiotherapy**

|  |   |   |
|--|---|---|
|  | 
indicator of patient respiratory tolerance to pulmonary radiotherapy than conventional lung function testing by determining the relationship between hyperpolarized Xe-129 MR imaging indices and functional patient outcome measures (dyspnoea and radiation-induced lung toxicity assessment).
 
To use functional lung information in virtual predictive and adaptive radiotherapy treatment planning.
 | 
Retrospective comparison of modified radiotherapy treatment planning incorporating functional lung information from hyperpolarized Xe-129 MR imaging with conventional radiotherapy treatment plans.
 |
|--|---|---|

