### **8.2. Inclusion Criteria**

- Participant is willing and able to give informed consent for participation in the trial.
- Male or Female, aged 18 years or above.
- Patients where radiotherapy or chemoradiotherapy (concurrent or sequential schedule) affecting the lung is considered appropriate by the treating clinical Oncologist.
- WHO performance status 0-2
- Able (in the Investigators opinion) and willing to comply with all study requirements.

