**9.7. Radiotherapy**

Radiotherapy treatment will be CT planned and delivered as per local departmental radiotherapy protocols. The treating Oncologist will not have access and be blinded to the baseline Xe-129 MRI images whilst planning radiotherapy. Entry into this study will not delay patients commencing radiotherapy, and their treatment will not be altered as a result of their enrolment into this study.

The appropriate beam energy will be selected to optimize the RT dose distribution in the target volume and minimize dose to non-target tissues.

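### The closer-correlation test in 12.1 tends to favour Xe-129, because FEV1 and gas transfer help decide who is accepted for radiotherapy and Xe-129 does not

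*Combined protocol and SAP*

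**What the plan says.** - **The test (12.1, under the superiority heading).** "We will test the hypothesis that Xe-129 lung MRI has a closer correlation with these measures than" FEV1 or gas transfer. The outcomes named are the Dyspnoea-12 and MRC scores. The section does not say whether baseline values, follow-up values or changes are correlated. Section 12.3 sets p<0.05.
- **The related secondary objective (section 6).** It seeks preliminary data on whether baseline Xe-129 is a more reliable "indicator of patient respiratory tolerance to pulmonary radiotherapy than conventional lung function testing".
- **How patients are accepted now (4.3).** "Currently assessment of patients for radiotherapy involves lung function measurements to provide a clinical indicator as to whether or not the patient would tolerate treatment". The same paragraph adds: "The current gold standard for assessment of lung function is spirometry and gas transfer". These are the comparators in 12.1.
- **Who enters (7.1, 8.2).** Patients for whom radiotherapy or chemoradiotherapy "affecting the lung is considered appropriate by the treating clinical Oncologist". The criteria contain no FEV1 or gas-transfer threshold.
- **Where Xe-129 comes in (7.1, 9.7).** The first scan follows enrolment, and "The treating Oncologist will not have access and be blinded to the baseline Xe-129 MRI images whilst planning radiotherapy".
- **Who has comparator data (7.1, 9.6).** Full pulmonary function tests are done only in patients with lung cancer.

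Nothing in 12.1 to 12.7 conditions the comparison on the acceptance decision, corrects for a restricted range, or limits the conclusion to accepted patients.

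**The concern.** The two measures are not compared on equal terms. Lung function has already been used to sort patients before enrolment and Xe-129 has not. Selecting on one predictor narrows its spread among those who remain and so lowers its correlation with outcome. A second predictor that played no part in selection loses less, unless it nearly duplicates the first. A closer correlation for Xe-129 could then arise partly because the comparator had already done its work.

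Two things are at stake. The first is whether a result reported under a superiority heading can be read as a property of the imaging. The second is the use suggested in section 5, that Xe-129 could inform suitability for radiotherapy better than current investigations. Patients refused on lung function are not in the data, so these data cannot show how Xe-129 would perform in that decision.

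**Working it through.** **No plan figure to reproduce.** The sample size of 30 (12.2) rests on feasibility. No expected correlation, effect size or power is given.

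**Inputs.** From the documents: n=30 in total and significance at 0.05 (taken as two-sided, since 12.3 does not say). Assumed, because the documents are silent:
- r, the true correlation (absolute value) of each measure with dyspnoea before selection: 0.5 for both, so the two are equally good;
- r12, the FEV1–Xe-129 correlation: 0.5, varied from 0.3 to 0.9;
- q, the share refused on FEV1: 0–50%.

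**Step 1: variance left after selection.** For a standard normal FEV1 cut at a = Φ⁻¹(q), let λ = φ(a)/(1−q). Then U = 1 + aλ − λ². At q=0.30: a=−0.524, λ=0.497, U = 1 − 0.260 − 0.247 = 0.493.

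**Step 2: correlations in accepted patients.**
- FEV1: r√U / √(1 − r²(1−U)) = 0.5×0.702/√0.873 = 0.38
- Xe-129: r(1 − r12(1−U)) / √[(1 − r²(1−U))(1 − r12²(1−U))] = 0.5×0.7465/0.873 = 0.43

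**Step 3: simulated trials.** Trials of n=30, 20,000 per scenario, using Williams' test for two dependent correlations on n−3 degrees of freedom:
t = (r_Xe − r_FEV1) √{(n−1)(1+r12) / [2((n−1)/(n−3))|R| + r̄²(1−r12)³]}, where |R| is the determinant of the 3×3 correlation matrix and r̄ is the mean of the two correlations.

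Results for r = r12 = 0.5:

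| Refused on FEV1 | U | r, FEV1 | r, Xe-129 | Xe-129 looks closer | Xe-129 falsely declared closer | FEV1 falsely declared closer |
|---|---|---|---|---|---|---|
| 0% | 1.000 | 0.50 | 0.50 | 50% | 2.4% | 2.6% |
| 10% | 0.712 | 0.44 | 0.46 | 55% | 3.4% | 1.8% |
| 20% | 0.583 | 0.40 | 0.44 | 58% | 3.7% | 1.6% |
| 30% | 0.493 | 0.38 | 0.43 | 61% | 4.6% | 1.3% |
| 50% | 0.363 | 0.33 | 0.41 | 65% | 5.7% | 0.9% |

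The percentages carry simulation error of a few tenths of a point.

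**Step 4: sensitivity.**
- r12=0.3, 30% refused: 0.38 against 0.46; Xe-129 looks closer in 67% and is falsely declared closer in 6.3%.
- r12=0.8, 30% refused: 0.38 against 0.39; 53% and 3.1%.
- r12=0.9, 30% refused: 0.376 against 0.379, almost no tilt.
- n=20 (some patients have no full pulmonary function tests), r12=0.5, 10–50% refused: 54–63% and 3.0–4.8%.
- Lung function at half weight in the decision (r12=0.5): the gap is 0.01 at 10% refused and 0.02–0.03 at 30–50%.
- Selection on dyspnoea alone: both correlations fall equally, so there is no tilt.
- Selection on FEV1 and dyspnoea together, 30% refused: 0.19 against 0.34, a larger tilt.

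**Step 5: the added-value coefficient.** With FEV1 in the model, the standardised Xe-129 slope is (r − r·r12)/(1 − r12²) = (0.5 − 0.25)/0.75 = 0.333. Selection on FEV1 does not change it, and it stayed at 0.333 at every selection fraction simulated. Its precision is poor. The residual variance is 1 − 2×0.5×0.333 = 0.667 and the variance of Xe-129 given FEV1 is 0.75. The standard error at n=30 is about √(0.667/(27×0.75)) = 0.18, giving 0.33 ± 0.37.

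**The case against.** The strongest reply is that the strength of selection is unknown. Eligibility rests on the oncologist's judgement plus WHO status 0–2, with no lung-function threshold, so hard truncation on FEV1 alone is near the worst case. At the planned p<0.05 the inflation is modest, and it almost vanishes when the two measures are highly correlated. The objective asks only for preliminary data. All of this stands, and it limits how strongly the point can be put. It does not remove a bias with a predictable direction under a heading that claims superiority.

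It is also true that no analysis can recover tolerance of radiotherapy in patients who do not receive it. That is a reason to narrow the conclusion.

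A reader might infer a second and larger bias. Only Xe-129 is withheld at planning (9.7), and section 4.1 says "The risk of developing RILT can be determined by assessment of the mean lung dose (MLD" and the irradiated lung volume, so lung function might also shape the lung dose and weaken the comparator further. The documents do not support this. No section says lung function sets the dose; 9.7 says planning follows departmental protocols. The direction would also have to be assumed. Suppose dose lowers tolerance by 0.4 SD per SD. If better FEV1 goes with more dose (0.4), the covariances with tolerance become 0.5 − 0.16 = 0.34 for FEV1 and 0.5 − 0.08 = 0.42 for Xe-129. If better FEV1 goes with less dose, they become 0.66 and 0.58, and the tilt favours FEV1. Section 12.1 also names only dyspnoea scores and no time point; for a baseline correlation, radiotherapy dose is irrelevant. Withholding Xe-129 from planning is sound in itself.

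**Conclusion.** The point holds for selection at acceptance. The comparator in 12.1 is part of the decision that determines who can be enrolled, Xe-129 is not, and the plan neither conditions on that decision nor limits the claim. To the extent that patients are refused on lung function, the head-to-head correlation leans towards Xe-129.

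The size is modest and cannot be fixed from the documents: under the assumptions in the table, about 55–65% of null trials show Xe-129 as closer, with a false-positive rate in its favour of about 3.4–5.7% instead of 2.5%. It is small if few are refused or if the FEV1–Xe-129 correlation is about 0.8 or higher. These figures are for correlations of levels; correlations of change may behave differently. The limit on interpretation applies whatever the size: these data cannot show that Xe-129 could replace lung function in deciding suitability.

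**What to change.** In section 12.1:

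1. Make the main comparison the added value of Xe-129 in a regression for dyspnoea that already contains FEV1 and gas transfer, and report the Xe-129 coefficient with its confidence interval. Selection on covariates in the model does not distort that coefficient. It would still be affected if acceptance also depended on breathlessness itself, and the report should say so. Keep the head-to-head correlations as descriptive results. A non-zero coefficient shows that Xe-129 adds information, not that it is the better test.
2. Replace the superiority heading with a conclusion limited to patients already accepted for radiotherapy, and make no claim that Xe-129 could replace lung function in deciding suitability.
3. State the number of patients with full pulmonary function tests, since the comparison may have fewer than 30.

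Adjustment for mean lung dose or V20 does not remove range restriction. It is at most an optional sensitivity analysis for follow-up outcomes.

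The cost is a wording change, one or two degrees of freedom in a small exploratory model with a wide interval, and a narrower claim. No new visits or scans are needed.
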